11.4. Safety Analyses

The primary safety endpoint in Part 1 and Part 2 are Adverse events, collected until the 42-day post-boost visit, serious adverse events and IREs, collected until the end of the study and solicited local and systemic adverse events (reactogenicity), collected until 7 days after each vaccination. Safety analyses will be conducted during the planned interim analyses, primary analysis and final analysis. In addition, safety analyses may be conducted during ad hoc interim analyses. For more details about the interim and final analyses, see Sections 11 and 11.6.

Safety data will be analyzed descriptively (including 95% confidence intervals, if applicable). In general, the primary safety plan will analyze each part separately and secondarily analyze the combined safety data from Part 1 with Part 2, Group 2 (MVA prime/Ad26 boost 0, 14-day regimen). In detail, safety data will be separately described by part, HIV infection status, and vaccination regimen (in Part 2 only). For purposes of estimating rates and confidence intervals, various combinations of those factors will be considered (including collapsing across parts for analyzing the adverse event profile of the MVA/Ad26 regimen).

Baseline for all safety parameters will be defined as the last value before the prime vaccination.

Exploratory statistical analyses may be considered comparing safety endpoints (such as proportion of subjects experiencing systemic reactogenicity) between active and placebo subjects within part, group and cohort or across groups and cohorts among active subjects (eg, comparing rates between healthy and HIV-infected subjects with a similar vaccination regimen). Such comparisons will be described in the SAP and will be considered exploratory as the study is not definitively powered to detect small differences in safety rates between vaccination regimens or infection status or formally prove equivalence between regimens. Instead the purpose of such a

comparison would be to identify any potential safety issue which could then be formally assessed for equivalence in a future study or considered in a meta-analysis combining data across multiple studies.

Adverse Events (Including Reactogenicity)

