2. GENERAL ANALYSIS DEFINITIONS

The type I error rate (α) is set to 0.05 and corresponding 2-sided 95% confidence intervals (CIs) will be calculated wherever applicable. Adjustment of the α (type I error) level due to multiplicity is not applicable for this study as no planned formal statistical hypothesis testing will be performed.

Analysis and evaluation are defined separately for each parameter later in this document together with the description of rules for handling missing or incomplete data. The analyses will include vaccinated subjects with respect to the actual vaccine administered. For instance, if a subject is randomized to the Ad26.ZEBOV followed by MVA-BN-Filo vaccination schedule but is inadvertently vaccinated according to the MVA-BN-Filo followed by Ad26.ZEBOV vaccination schedule, the subject will be included in the latter vaccination schedule. Also, subjects who receive only the first (dose 1) vaccination will be included in the vaccination schedule with the corresponding dose 1 vaccine. On the other hand, subjects who will receive a homologous regimen (ie, Ad26.ZEBOV followed by another Ad26.ZEBOV or MVA-BN-Filo followed by another MVA-BN-Filo) will be excluded from summary analyses (ie, tables and graphs) and listed separately.

In general, the study data will be analyzed as follows:

- Categorical variables will be summarized with a frequency table presenting counts and percentages.

- Continuous variables will be summarized using the following statistics, as appropriate: number of observations, arithmetic mean, geometric mean, corresponding 95% confidence interval (CI), standard deviation, standard error, median, quartiles (Q1 and Q3), minimum and maximum.

Baseline value will be defined as the value of the last available assessment performed prior to dose 1 administration, unless specified otherwise.

For safety assessments, the *baseline value* will be an assessment performed prior to or on the date (only if time of assessment is missing) of the dose 1 administration. The baseline value for immunogenicity assessments will be an assessment performed before or on the date of dose 1 administration. In case of multiple values, the value closest to the vaccination will be used as the baseline.

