Reference value (only for immunogenicity) will be defined as the assessment performed on the date of the dose 2 vaccination. In case of multiple values (on the same day of vaccination), the value closest to the vaccination will be used as the reference value.

Visit day will be determined relative to the actual day of vaccination (date of dose 1 administration or date of dose 2 administration).

Repeated assessments of immunogenicity and safety (including HIV viral load and CD4+ cell counts in HIV-infected subjects) will be allocated to analysis windows and periods based on [Table 2](#) and [Table 3](#), as described below.

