Day 380 (365 days Post-dose 2)	[336; 396]	≥ 274	366
Day 394 (365 days Post-dose 2)			

^a The analysis based on the per protocol (PP) analysis set will be restricted to data points that fall within this window (ie, protocol-defined window).

^b The analysis based on the immunogenicity analysis set will be restricted to data points that fall within this window.

Note 1: The analysis windows and target days are based on the relative day (ie, with respect to reference day [day of dose 1 or dose 2 administration]).

Note 2: Day of dose 2 is also considered as Day 1 with respect to the second vaccination (ie, for calculating target days that fall after the second vaccination).

Note 3: Day 36, Day 57, Day 195 and Day 380 apply only to the 14-day interval vaccination schedule. While Day 50, Day 71, Day 209 and Day 394 apply only to the 28-day interval vaccination schedule.

Table 3: Analysis Periods

Phase	Period	Interval	
		From	To
Screening		00:00 on the date of signing the informed consent form	One minute prior to dose 1 administration on Day 1
Regimen*	Post-dose 1	Date and time of dose 1 administration	Minimum of: 
 a) 23:59 on the date of last contact (for early study discontinuation) b) 23:59 on the date of relative Day 29 Post-dose 1 c) 23:59 on planned visit day of dose 2 administration (in case dose 2 is not administered) d) one minute prior to dose 2 administration [□] e) 23:59 on the date of database cut-off (in case of interim analysis)
Post-dose 1 FU		One minute after the end of the Post-dose 1 period	Minimum of: 
 a) 23:59 on the date of last contact (for early study discontinuation or completion) b) one minute prior to dose 2 administration c) 23:59 on the date of database cut-off (in case of interim analysis)
Regimen*	Post-dose 2	Date and time of dose 2 administration	Minimum of: 
 a) 23:59 on the date of last contact (for early study discontinuation or completion) b) 23:59 on the date of relative Day 29 Post-dose 2 c) 23:59 on the date of database cut-off (in case of interim analysis) 
Note: subjects who do not receive dose 2 will not have a Post-dose 2 period.

Post-dose 2 FU		One minute after the end of the Post-dose 2 period	Minimum of: 
 a) 23:59 on the date of database cut-off (in case of interim analysis) b) 23:59 on the date of last contact (for early study discontinuation or completion)

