7.3.1. Definitions

In determining toxicity grades, the following rules will be applied:

- Worst grades/abnormalities are determined over the entire period (eg, Post-dose 1 or Post-dose 2) separately, including all post-baseline measurements of the corresponding period.
- The abnormalities “abnormally low” and “abnormally high” are considered equally important and both abnormalities are shown in the tables. (This means that the sum of the percentages can exceed 100%).
- If a laboratory value falls within the grading as specified in the grading table but also within the local laboratory normal limits, the value is considered as normal or Grade 0.
- Laboratory results falling between the grading scales will be allocated to the adjacent worst-case grade (because the scale for some parameters in the grading table is not continuous as there may be zones where toxicity grade definitions do not exist).

An abnormality (toxicity grade or abnormality based on normal ranges) will be considered as following vaccination in a period and/or phase if it is worse than the corresponding baseline record. If the baseline value is missing, the abnormality is always considered as following vaccination. A shift from “abnormally low” at baseline to “abnormally high” post-baseline (or vice versa) is also considered as an abnormality following vaccination.

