7.3.3. Analysis Methods

Laboratory abnormalities will be determined in accordance with the toxicity grading tables (Attachments 3 and 4), and in accordance with the normal ranges of the clinical laboratory. The worst abnormalities following vaccination will be summarized (ie, showing number and percentage) by vaccination schedule and presented per period/phase, with special attention to Grade 3 toxicities. Focus will be on clinical abnormalities that occur during Post-dose 1 and Post-dose 2 periods, as well as the Regimen period (ie, combined Post-dose 1 and Post-dose 2 periods). Similar tables for worst abnormalities will be provided pooled by vaccine (dose). A listing will also be provided for subjects with clinically significant abnormal laboratory findings.

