7.4. Vital Signs and Physical Examination Findings

Vital sign abnormalities will be determined in accordance with the DMID Vital Signs Toxicity Grading (Attachment 3). The worst abnormalities (following vaccination) of vital signs will be tabulated (ie, showing number and percentage) and listed. Focus will be on the abnormalities that occur during the Post-dose 1 and Post-dose 2 periods, as well as the Regimen period (ie, combined Post-dose 1 and Post-dose 2 periods).

It is important to note that a full physical examination is only conducted at screening. At other visits, only abbreviated, symptom-directed examinations are performed per the investigator's discretion. Therefore, only a listing of subjects with clinically significant physical examination findings (ie, abnormalities) will be provided.

Also, any clinically relevant vital signs or physical examination abnormalities occurring from signing of the ICF onwards until 42-day post dose 2 vaccination are recorded on the AE page of the eCRF and will be analyzed as AE.

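### Post-dose 2 laboratory abnormalities are judged only against the pre-dose 1 value, so abnormalities already present before dose 2 are counted again under dose 2 and in the by-vaccine tables

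*SAP*

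**What the plan says.** **Baseline.** SAP 2 states: "Baseline value will be defined as the value of the last available assessment performed prior to dose 1 administration, unless specified otherwise". Protocol 11.4 says the same for safety: "Baseline for all safety parameters will be defined as the last value before the prime vaccination". SAP 7.3 specifies nothing different for laboratory tests.

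**Pre-dose 2 comparator.** SAP 2 does define one, but limits its use: "Reference value (only for immunogenicity) will be defined as the assessment performed on the date of the dose 2 vaccination".

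**Flagging rule.** SAP 7.3.1 states: "Worst grades/abnormalities are determined over the entire period (eg, Post-dose 1 or Post-dose 2) separately". Within a period, an abnormality is "considered as following vaccination in a period and/or phase if it is worse than the corresponding baseline record".

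**Presentation.** SAP 7.3.3 tabulates the worst abnormalities by schedule for Post-dose 1, Post-dose 2 and the combined Regimen period, and adds tables pooled by vaccine (dose). For vital signs, SAP 7.4 says: "The worst abnormalities (following vaccination) of vital signs will be tabulated (ie, showing number and percentage) and listed". It covers the same periods but does not restate the rule.

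**Sampling.** The protocol's Time and Events Schedule places chemistry and hematology on Day 1, Day 8, the boost day (Day 15 or 29) and 7 days after the boost (Day 22 or 36). Blood is drawn and vital signs are measured before each vaccination. In SAP Table 3 the Post-dose 1 period ends no later than "one minute prior to dose 2 administration", so a timed boost-day sample falls before the Post-dose 2 period.

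**The concern.** The Post-dose 2 laboratory table rests mainly on one scheduled sample, taken a week after a pre-dose 2 sample that the rule ignores. A result that was abnormal before dose 2 and has not changed since says nothing about dose 2, yet it is tabulated as following vaccination in that period.

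The by-dose and by-vaccine tables are where a reader looks to see what each component does. In both regimens dose 2 is the other vaccine, so carry-over from the first vaccine appears under the second. In Part 2, MVA-BN-Filo is dose 2 for 320 of the 400 planned active subjects (80%). If the by-vaccine tables combine dose positions, most MVA-BN-Filo observations follow Ad26.ZEBOV. The placebo columns allow for background persistence, but not for persistence of an effect of the first active vaccine.

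Unsolicited adverse events are handled differently: SAP Attachment 1 allocates them by start date. Laboratory and adverse event tables for the same period would then follow different attribution rules.

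**Working it through.** **Step 1. Can the corresponding baseline record be read as period-specific?** No. SAP 2 sets the general baseline before dose 1, protocol 11.4 sets it before the prime for all safety parameters, and the only dose 2 reference is confined to immunogenicity.

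**Step 2. Apply the rule to toxicity grades.**

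| Pre-dose 1 | Pre-dose 2 | Post-dose 2 | Flagged Post-dose 1 | Flagged Post-dose 2 (SAP) | Worse than both earlier values |
|---|---|---|---|---|---|
| 0 | 1 | 1 | yes | yes | no |
| 0 | 2 | 1 | yes | yes | no |
| 0 | 1 | 2 | yes | yes | yes |
| 0 | 0 | 1 | no | yes | yes |
| 0 | 1 | 0 | yes | no | no |
| 1 | 1 | 1 | no | no | no |

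The first two rows are the problem; in the second the subject improved after dose 2. The last two rows show the limits: abnormalities that have resolved, or that were at the same grade before dose 1, are not counted after dose 2. In the Regimen period a subject in the first two rows is counted once, correctly.

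Hemoglobin shows the mechanism plainly. It is graded only as a change from baseline, so a fall after dose 1 that persists is graded again after dose 2.

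**Step 3. Possible size.** The plan gives no figure to reproduce, so these inputs are assumptions:

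- p, the share with an abnormality that arose after dose 1 and is present before dose 2: 5-15%
- s, the chance that it is still present 7 days after dose 2: 30-50%
- q, the true rate of new or worsened abnormalities after dose 2: 5%

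Reported Post-dose 2 rate = p·s + (1 − p·s)·q. Carry-over share = p·s / reported rate.

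| p | s | p·s | Reported rate | Carry-over share |
|---|---|---|---|---|
| 5% | 30% | 0.015 | 0.015 + 0.985 × 0.05 = 0.06425 | 23% |
| 5% | 50% | 0.025 | 0.025 + 0.975 × 0.05 = 0.07375 | 34% |
| 10% | 30% | 0.030 | 0.030 + 0.970 × 0.05 = 0.0785 | 38% |
| 10% | 50% | 0.050 | 0.050 + 0.950 × 0.05 = 0.0975 | 51% |
| 15% | 30% | 0.045 | 0.045 + 0.955 × 0.05 = 0.09275 | 49% |
| 15% | 50% | 0.075 | 0.075 + 0.925 × 0.05 = 0.12125 | 62% |

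For the 40 active subjects per cohort in Part 2 Group 2, the reported count would be 2.6 to 4.9 (40 × 0.06425 to 40 × 0.12125), against 2.0 (40 × 0.05) new or worsened.

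**Step 4. Sensitivity.** The formula counts every persisting abnormality as carry-over, including the few that also worsen. Removing those at the 5% rate (multiplying p·s by 0.95 in the numerator) moves the ends to 22% and 59%. With q = 2% the ends become 0.015/0.0347 = 43% and 0.075/0.0935 = 80%. A higher q or a lower s reduces the share, which goes to zero as s does.

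**The case against.** **The worst cases are screened out.** Protocol 6.3 bars the boost for a persisting clinically significant abnormality considered related to the prime, and SAP Table 3 gives subjects without dose 2 no Post-dose 2 period. This stands. What remains is abnormality judged not clinically significant or not related, which the graded tables still count.

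**Carry-over may be small.** Protocol 1.1 describes the events in the first Phase 1 study as transient. It also says that, in pooled data from two studies, hypokalemia and neutropenia occurred in similar numbers after MVA-BN-Filo and placebo. Its neutrophil figures (8% and 17%) are adverse events from 7-day post-prime data with active and placebo combined, so they do not give prevalence at Day 15 or 29. This also stands, and it means no size can be claimed from the documents.

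**The consequence is limited.** The objectives concern regimens, the primary safety endpoints are adverse events rather than laboratory grades, and no formal testing is planned. Clinically relevant laboratory changes are also recorded as adverse events and allocated by start date. This is partial mitigation, but it does not correct the graded tables that SAP 7.3.3 puts in focus.

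**The pre-dose 1 value is the only one free of vaccine exposure.** Requiring a result to be worse than both values would hide an abnormality that dose 2 sustains at the same grade. This is fair, and is why both versions should be shown.

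**Stronger readings that the documents do not support.** A reader might infer that:

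- Abnormalities are moved to the wrong vaccine. One measured before dose 2 is normally counted under dose 1 as well, so it is counted twice rather than moved.
- The 14-day schedule suffers more, because its post-dose 2 sample falls about 21 rather than 35 days after dose 1. The first vaccine also differs between schedules, so the direction is undetermined.
- Vital signs are certainly affected. SAP 7.4 uses the same concept but does not restate the rule, and the tables pooled by vaccine (dose) are specified for laboratory data and adverse events only.

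**Conclusion.** The point holds for laboratory tests as a matter of definition and needs no assumption. Under SAP 7.3.1, an abnormality that arose between the doses and is still worse than the pre-dose 1 value after dose 2 is reported again in the Post-dose 2 and by-vaccine tables, even when it is stable or improving. The Regimen summary is sound. For vital signs the same follows only if the 7.3.1 rule is meant to apply there.

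The 23-62% carry-over share is illustrative and rests wholly on the assumed prevalence, persistence and new incidence. Transience of the events and the boost contraindication both point to a lower share. This is a worthwhile, inexpensive improvement to descriptive safety tables; it does not undermine the primary safety endpoints.

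**What to change.** 1. In SAP 2 and 7.3.1, define the last value before dose 2 as a reference value for laboratory safety data.
2. In the Post-dose 2 and by-vaccine laboratory tables, show separately (a) abnormalities worse than both the pre-dose 1 and pre-dose 2 values, that is, new or worsened after dose 2, and (b) abnormalities worse than baseline that were already present before dose 2. For hemoglobin, keep grading as change from the pre-dose 1 value and compare those grades.
3. Keep the worse-than-baseline version alongside, in line with protocol 11.4, and use it alone for the Regimen period.
4. Where the pre-dose 2 value is missing, use the pre-dose 1 baseline.
5. State in SAP 7.4 whether the 7.3.1 rule governs vital signs; if so, apply the same split.
6. Record the change in SAP 3, because the protocol fixes the safety baseline before the prime.

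**Cost.** One derived flag and a footnote explaining that the columns use different references. No new data are needed, since the pre-dose 2 sample is already scheduled. The drawback is that an abnormality sustained by dose 2 at an unchanged grade falls in category (b) and is not counted as new; showing both versions keeps it visible.

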7.3.2. Data Handling Rules

In case a laboratory test result is *censored* (no numeric value is available, but only a verbatim term) then a numeric value will be imputed:

- For integer x :
 - If the value is $<x$ then impute with $x-1$.
 - If the value is $>x$ then impute with $x+1$.
- For mantissa (decimal part) x :
 - If the value is $<y.x$ then impute with $y.x-0.1$ (if x has 1 decimal place of precision).
 - If the value is $>y.x$ then impute with $y.x+0.1$ (if x has 1 decimal place of precision).

Remark: The value added or subtracted from the mantissa should follow from its mantissa.

Example:

If value is <5 or >10 impute with 4 and 11 respectively.
If value is <5.3 or >10.7 then impute with 5.2 and 10.8 respectively.
If value is <5.32 or >10.73 then impute with 5.31 and 10.74 respectively.

7.3.3. Analysis Methods

Laboratory abnormalities will be determined in accordance with the toxicity grading tables (Attachments 3 and 4), and in accordance with the normal ranges of the clinical laboratory. The worst abnormalities following vaccination will be summarized (ie, showing number and percentage) by vaccination schedule and presented per period/phase, with special attention to Grade 3 toxicities. Focus will be on clinical abnormalities that occur during Post-dose 1 and Post-dose 2 periods, as well as the Regimen period (ie, combined Post-dose 1 and Post-dose 2 periods). Similar tables for worst abnormalities will be provided pooled by vaccine (dose). A listing will also be provided for subjects with clinically significant abnormal laboratory findings.

